RESEARCH PROTOCOL

Date	January 9, 2017
Title	Using Intraoperative Sensing Technology to Evaluate Revision TKA
Research Sponsor	OrthoSensor, Inc., Dania Beach, FL USA
Principal Investigator	[name]
Department	The Leone Center for Orthopedic Care, Holy Cross Hospital, Fort Lauderdale, FL USA

Project Summary/Abstract

This study will attempt to draw relationships between the soft-tissue related complications contributing to early TKA revision and the loading and positional patterns from intraoperative tibial trial sensors. The data from the sensors may enable the surgeon to address such soft-tissue abnormalities that may otherwise be unknown during traditional total knee revision procedures. The utilization of sensors should in theory, help diagnose the potential causes attributing to soft-tissue imbalance and may lead to a decreased need for an all component revision. Furthermore, the economic implications from converting a total revision to a partial revision could have a profound effect to the patient and healthcare provider such as decreased rehabilitation regimes and opportunity for cost savings. Eligible revision patients who agree to participate will be followed for a period of 12 months following the revision procedure. Patient reported outcomes measures (PROM) such as the 2011 Knee Society Score (KSS) and the Veterans Rand 12-Item Health Survey (VR-12) will be collected at baseline (pre-operatively) and at 6 weeks, 6 months and 12 months post-procedure. All outcomes will be scored to observe changes from baseline at 12-months. Cost-analyses of sensor-assisted revision TKA will be performed to include OR costs, facility and physician fees, as well as payments to post-acute collaborators such as SNFs, rehab hospitals, PT and home care providers. A quantitative analysis of commercial payer claims / usage data (e.g., CMS Medpar data) will be used to examine costs associated with traditional revision TKA procedures.

Purpose of Study

A. Research Objective:

Primary: The objective is to evaluate and link the possible causes of early TKA revision procedures using intraoperative sensors in effort to understand why knees fail in addition to examining the economic implications to the patient and hospital.

Secondary: To observe changes in patient reported outcome measures from baseline at 12-months. Patients will be stratified by diagnosis and revision type (partial / total) to observe changes in outcome measures.

B. Hypothesis or Research Question

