However, the use of advanced technology to understand why total knee arthroplasties fail today has not been extensively evaluated. A recent development has made it possible to embed microelectronics into the standard tibial trial (VERASENSE, OrthoSensor, Inc., Dania Beach, FL). This array of sensors provides dynamic, intraoperative feedback regarding tibiofemoral position and quantitative pressure at peak contact points in the medial and lateral compartments during total knee arthroplasty (TKA) trialing. Using sensor-derived data, the surgeon can now evaluate intercompartmental loading throughout the range of motion (ROM) and correct for soft-tissue abnormalities while receiving real-time feedback regarding joint position and the tibiofemoral relationship defined by the contact point location. Utilization of these sensors during revision TKA should in theory, help diagnose the potential causes of revision if they relate to soft tissue imbalance.

Research Plan

A. Study Design

- Prospective, multicenter, single-cohort evaluation of patients undergoing sensor-assisted revision total knee arthroplasty
- All eligible patients will be asked to participate and sign informed consent
- The surgeon will use Verasense on all patients. Data will be electronically captured by designated research personnel.
- Patients will be assessed preoperatively and will have standard of care follow up appointments at 6 weeks, 6 months and 12 months.
 - During these visits the following outcome measures will be assessed:
 - ✓ New Knee Society Score (KSS)⁷
 - ✓ The Veterans Rand 12-Item Health Survey (VR-12)

B. Setting

The study will be conducted at institutions within the United States.

C. Participants: Patients requiring revision total knee arthroplasty will be recruited from the respective clinical practice at the participating institutions. Up to 200 patients will be enrolled and followed for a period of 12 months in order to assess patient outcomes. Any patient who is a candidate for revision TKA and meets all inclusion and no exclusion will be offered study participation without regard to race, sex, economic status, or religious belief.

Inclusion criteria:

- Patients undergoing revision unilateral total knee arthroplasty within the first 5-years of the index procedure
 - a. Include Male and Female subjects
 - b. Include subjects 18 years and older

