- Demos/History/Clinical: Patient's age at time of surgery, gender, ethnicity, height/weight and body mass index, occupational status, health insurance type, tobacco and alcohol use. Patients medical history and comorbidities will be obtained as well as principal / secondary diagnosis and pre-operative plan for revision (i.e., total revision, partial revision). Preoperative radiographs (AP, lateral and skyline views) should be taken as standard of care.
- Intra-operative /discharge data: OR and tourniquet times, surgical technique and approach, operative complications (if applicable), length of stay and discharge destination. Pre and post-revision sensor data will be obtained (operative findings / operative action/surgical correction). Length of stay and discharge status will be captured as well as any post-operative complications and readmissions within 90 days of discharge following the revision procedure.
- Clinical Outcome Measures: Dependent variables or outcome variables will be collected pre-operatively and at 6 weeks, 6 months and 12 months post-operatively. The outcomes measures will include the 2011 Knee Society Score and THE VETERANS RAND 12-ITEM HEALTH SURVEY (VR-12).
- Cost Data: Hospital cost data including OR costs, facility and physician fees, as well as payments to post-acute collaborators such as SNFs, rehab hospitals, PT and home care providers will be collected. MEDPAR data from Centers for Medicare and Medicaid (CMS) will be used as benchmark to understand the national averages of hospital cost, hospital charges and average reimbursement. Implant cost data will be obtained from literary sources and market reports.

Data Sheet: See attached data sheets.

E. Study Device

Verasense™ is developed by Orthosensor Inc., Dania Beach, Florida, USA and is FDA approved for commercial distribution in the United States. The 510(k) number is K090474.

F. Statistical Analysis

Analysis of the data will be performed using SPSS version 21. Comparative Statistics will be run between outcomes data stratified by revision type: Analysis of variance (AVOVA) will be used to assess the difference between groups stratified by reasons for revision, with post-hoc TUMHANE'S test to demonstrate significance. Separate analyses will be performed to evaluate power of sample sizes and any correlative affect that demographic/clinical variables may have on patient outcomes. The alpha value is 0.05 with a lower power threshold of 0.7.

G. Ethical Considerations

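### Section F has no rule for missing 12-month scores and no use for the 6-week and 6-month scores, so the 12-month PROM comparison is completers-only by default

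*Combined protocol and SAP*

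**What the plan says.** **Target.** The Project Summary states: "All outcomes will be scored to observe changes from baseline at 12-months". The secondary objective (Purpose of Study, A) repeats it, "To observe changes in patient reported outcome measures from baseline at 12-months", and adds the grouping: "Patients will be stratified by diagnosis and revision type (partial / total) to observe changes in outcome measures".

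**Collection.** Under Research Plan, A. Study Design, patients "will have standard of care follow up appointments at 6 weeks, 6 months and 12 months", and KSS and VR-12 are assessed at those visits. Section D (Data Collection) confirms the schedule: "Dependent variables or outcome variables will be collected pre-operatively and at 6 weeks, 6 months and 12 months post-operatively".

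**Analysis.** Section F names ANOVA with a post-hoc test, which "will be used to assess the difference between groups stratified by reasons for revision". For revision type it promises comparative statistics of no named kind. It does not name the ANOVA's response variable or time point, define an analysis set, or say what happens to a patient without a 12-month score. It mentions no repeated-measures model, imputation or sensitivity analysis, and gives the 6-week and 6-month scores no role. The error levels are set in one line: "The alpha value is 0.05 with a lower power threshold of 0.7".

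**Size.** Section C (Participants): "Up to 200 patients will be enrolled and followed for a period of 12 months in order to assess patient outcomes". No expected dropout is given. The attached data sheets were not available for this review, and nothing here depends on what they contain.

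**The concern.** Change from baseline at 12 months cannot be computed without a 12-month score. An ordinary ANOVA on that change therefore omits anyone who missed the last visit, even if two post-operative scores are on file. As the scores are tied to standard-of-care appointments, some loss by 12 months is to be expected.

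Two things are at stake. The first is precision, since information already collected is not used. The second is bias. If staying in follow-up is related to how the knee is doing, the completers do not represent the enrolled patients, and the mean change, which the secondary objective sets out to observe, is distorted. The contrasts by diagnosis and by revision type can be distorted as well, but that needs a further condition. The groups are not randomised: under Methods/Procedures the surgeon settles on a partial or total revision in the light of case complexity and sensor output. So nothing in the design makes dropout alike across groups.

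**Working it through.** **The plan's own figure.** The ceiling of 200 cannot be reproduced. The documents give no effect size, SD, group sizes or dropout rate.

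**Inputs.** From the documents: at most 200 patients, alpha 0.05, power threshold 0.7. Assumed: two equal groups, two-sided test, SD of change 20 points, 6- to 12-month correlation ρ of 0.7 or 0.5, dropout after 6 months of 10% to 30%.

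**1. Precision under random loss.** With a fraction p observed at 12 months and everyone observed at 6 months, the effective sample size when the 6-month score is used is N / [(1 − ρ²)/p + ρ²]. For N = 200 and p = 0.8:

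- completers only: 200 × 0.8 = 160
- ρ = 0.7: 200 / (0.51/0.8 + 0.49) = 200 / 1.1275 = 177
- ρ = 0.5: 200 / (0.75/0.8 + 0.25) = 200 / 1.1875 = 168

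The difference detectable with 70% power, in SD units, is (1.960 + 0.524) × √(4/N). This gives 0.351 at N = 200, 0.393 at 160, 0.373 at 177 and 0.383 at 168. The 6-month score thus recovers about half of the loss at ρ = 0.7 (0.020 of 0.042) and about a quarter at ρ = 0.5 (0.010 of 0.042).

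**2. Bias in a group's mean.** Let leaving follow a logistic model in the 6-month score, with odds 2.7 times higher per SD of worse score. At SD 20 the completer mean change is then too high by:

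| Dropout | ρ = 0.7 | ρ = 0.5 |
|---|---|---|
| 10% | 1.3 points | 0.9 points |
| 20% | 2.5 points | 1.7 points |
| 30% | 3.5 points | 2.5 points |

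A separate large simulation at ρ = 0.6 and 20.7% dropout gave 0.107 SD, or 2.1 points at SD 20. Rescaled to ρ = 0.7 this is 2.1 × 0.7/0.6 = 2.5, in agreement. If patients who do well are the ones who stop attending, the sign reverses.

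**3. Bias in the contrast.** This is the difference between the two groups' biases. Simulated results with no true difference, 100 per group, ρ = 0.7:

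| Dropout pattern | False difference | False-positive rate |
|---|---|---|
| Same mechanism, same rate (10%, 20%, 30%) | −0.01, 0.02, 0.11 points | 5.0–5.2% |
| Same mechanism, 15% vs 25% | 1.0 point | 6.4% |
| Same mechanism, 10% vs 20% | 1.2 points | 6.5% |
| Same mechanism, 10% vs 30% | about 2.3 points | about 11% |
| Score-driven in one group, random in the other, 20% in each | 2.5 points | 12.7% |

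The rows agree with step 2: 2.5 − 1.3 = 1.2 for 10% vs 20%, and 3.5 − 1.3 = 2.2 for 10% vs 30%. A repeat of the last row gave 2.4 points and 12.1%, which is within simulation error. For the same one-sided pattern, 10% and 30% loss gave 1.3 and 3.5 points.

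A true difference matters as well. At ρ = 0.6, with the same mechanism in both groups and a true difference of 0.50 SD, the completer contrast was 0.470 SD. Dropout unrelated to outcome gave no bias even at unequal rates (10% vs 27%: 0.503 against a true 0.502).

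**4. Using the 6-month score.** In the same large simulation, an estimate that used the 6-month score by group returned the true contrast in every scenario where leaving depended on that score. Examples are 0.500 against 0.500, 0.497 against 0.499 (completers 0.388), and 0.000 against 0.001 (completers 0.098).

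**The case against.** The strongest reply is that the plan states no completers rule. Section F does not say what the ANOVA is run on; the 12-month change comes from the Project Summary and the secondary objective. ANOVA is also attached only to reasons for revision, not to partial versus total. Both points stand. Completers-only is a default consequence of a 12-month change target with no missing-data rule, and should be described as such. The gap and the remedy are the same either way.

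A reader might infer that if poor results drive patients away, the group comparisons are biased. The documents do not support that inference, and the arithmetic contradicts it: with the same mechanism, rate and true change in both groups, the contrast bias is about zero although both means are off. A reader might also infer that completers must look too good. Satisfied patients may equally skip a routine visit, and the documents settle neither the direction nor the size.

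It is also fair that the one-sided scenario is extreme, and that two groups of 100 are a simplification of an ANOVA over several diagnoses. It should be read as an upper case, with the unequal-rate rows as the milder ones.

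Finally, PROM change is a secondary objective in a study that describes itself as observational and not hypothesis driven. That limits the weight of the point. It does not remove it, because the plan still sets an alpha and compares groups.

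**Conclusion.** The point holds as a gap in the analysis plan for the secondary objective, and it should be corrected. With no missing-score rule and no role for the interim scores, a patient without a 12-month score drops out of the 12-month comparison.

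The loss of precision follows from any dropout, provided the 6- and 12-month scores are correlated: 160 against 177 or 168 at an assumed 20% random loss. Bias in each group's mean follows only if leaving depends on the scores. Bias in the contrasts follows only if, in addition, the groups differ in dropout rate, dropout mechanism or true change. That is possible in non-randomised groups but is not shown by the documents. At SD 20 and correlation 0.7 the false difference is about 0 when the groups are alike, about 1 point for a 10-percentage-point dropout gap, and about 2.5 points at 20% loss in the one-sided case. The SD, correlation, dropout rates and mechanisms are all assumptions.

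**What to change.** In Section F, make the main 12-month comparison a mixed model for repeated measures, for reason for revision and likewise for revision type:

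- **Outcomes:** the 6-week, 6-month and 12-month scores.
- **Terms:** baseline score, group, visit and group-by-visit, with an unstructured covariance.
- **Patients:** everyone with at least one post-operative score.
- **Report:** the 12-month group means and contrasts, with the number of patients who have a 12-month score in each group.
- **Sensitivity analyses:** the completer ANOVA, and a simple not-at-random analysis that shifts the 12-month values of patients without a score up and down, by group. The completer ANOVA alone does not test not-at-random loss.

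The cost is a few lines of plan text and slightly more analysis work, with no added patients, visits or data. The model assumes that scores are missing at random given the observed ones, which is why the second sensitivity analysis is needed. Multiple imputation using the interim scores would be an acceptable alternative. Collecting missed questionnaires remotely would help, but it adds a contact procedure and is optional; the fix does not depend on it.

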- a. **Informed consent:** Research assistants/coordinators will obtain patient consent and the consent statements will be kept in a secure location. Copy of the informed consent statement is attached.
- b. **Privacy information:** The data will be stored electronically on a restricted access network folder and will only be accessible to the investigator and research team. The information collected does not include information that may be damaging to the individual should it be wrongfully disclosed. Data sheets may be used in the collection of data, however, will not document PHI. Data analysis will be performed using only the de-identified database. No data will be disclosed to another institution and all identifiers linking to the patient will be destroyed after data collection is complete.
- c. **Confidentiality and Management of Data:** The data will be stored and will only be accessible to the investigator, research team and OrthoSensor. Data sheets may be used in the collection of data, however, will not document PHI. Data analysis will be performed using only the de-identified data. Information about study subjects will be kept confidential and managed according to the requirements of the Health Insurance Portability and Accountability Act (HIPAA). Patient data will be entered into electronic spreadsheets. One spreadsheet (the correlation tool) will contain the patient name, medical record number, and patient study number. The second spreadsheet will contain the patient study number, as well as all of the variables required by the study. The two spreadsheets will be stored as separate files. De-identified data will be provided to the Research Specialist for data analysis. Any paper records will be stored in hard copy in a locked filing cabinet for a minimum of five years. At this time the information will be shredded.
- d. **Risks/Benefits of participation:** There are no risks to participants. This study is intended for observational purposes only. There are no costs to exceed those associated with the standard of care which currently exists. This could potentially benefit those patients who are undergoing traditional revision TKA but this is not yet known.

H. Estimated Period of Time to Complete

When will study begin?	February 2017
IRB Approval	3 weeks
Data collection	~2 years
Data analysis	1 month
Presentation development (if applicable)	1 month
Manuscript Development (if applicable)	3 months

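### The cost lists for sensor-assisted revision do not name the VERASENSE insert, so its price could go uncounted in every patient

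*Combined protocol and SAP*

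**What the plan says.** Purpose of Study, A. Research Objective makes economics part of the primary objective: the causes of early revision are to be studied "in addition to examining the economic implications to the patient and hospital". The Project Summary expects that turning a total revision into a partial one could bring "decreased rehabilitation regimes and opportunity for cost savings".

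The cost components are listed twice. The Project Summary states "Cost-analyses of sensor-assisted revision TKA will be performed to include OR costs, facility and physician fees", and then adds payments to post-acute providers. D. Data Collection, Cost Data, has "Hospital cost data including OR costs, facility and physician fees, as well as payments to post-acute collaborators". Implants have a separate source: "Implant cost data will be obtained from literary sources and market reports".

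The comparator is external. In the Project Summary, payer claims and usage data, with MEDPAR as the example, "will be used to examine costs associated with traditional revision TKA procedures". In Cost Data, MEDPAR "will be used as benchmark to understand the national averages of hospital cost, hospital charges and average reimbursement".

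Under A. Study Design, the surgeon uses VERASENSE in every patient. Methods/Procedures has it used twice per case: once with the existing components in place and again for final balancing. E. Study Device identifies the sponsor as its developer. The text available gives no price for the insert, names no payer and has no rule for counting it. F. Statistical Analysis contains no costing method or perspective.

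**The concern.** The technology under evaluation is the one resource that the cost lists do not mention. It cannot be assumed to arrive through another heading. Implants, the other device cost, are priced outside the hospital data, and a device made by the sponsor may reach the site without an invoice. A hospital ledger can be complete and still show zero for something the hospital did not buy.

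The direction of the resulting error is known. An insert left out lowers the sensor-assisted side only, in every patient, and so favours the sponsor's product. The benefit the protocol anticipates arises only in patients whose planned total revision becomes partial. A cost that falls on everyone is therefore the one at risk of being missed, while a benefit that falls on some is counted.

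**Working it through.** The plan has no cost figure to reproduce: it gives no sensor price, expected saving or conversion rate. The check is to follow the insert through the stated cost streams.

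**Inputs from the protocol.** The sensor is used in 100% of patients (A. Study Design). Enrolment is at most 200 (C. Participants). The cost components are those in the Project Summary and Cost Data. The comparator is traditional revision from claims or MEDPAR data.

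**Inputs not in the protocol, kept as symbols.** S is the price of one insert. k is the number of inserts used per patient. q is the share of patients whose hospital OR costs already include the insert.

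1. **Error per patient.** Let C be all other costs. The full cost is C + kS.
   - If the hospital buys the insert and books it to OR costs, the record shows C + kS and the error is 0.
   - If the insert is supplied or not billed, the record shows C and the error is −kS.

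2. **Error over the study.** The mean understatement is (1 − q) × kS, and the total at full enrolment is 200 × (1 − q) × kS. With k = 1:
   - q = 1: 200 × 0 × S = 0
   - q = 0.5 (assumed, sites differ): 200 × 0.5 × S = 100S
   - q = 0: 200 × 1 × S = 200S

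   Methods/Procedures matches the first insert to the existing implant and allows a complete revision to the preferred system. Some cases might therefore need a second insert type (k = 2). That is an inference, but it is a reason to record the number used.

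3. **Whether it cancels.** Against a traditional-revision benchmark B, which the protocol treats as carrying no sensor, the true difference is C + kS − B and the recorded one is C − B. The whole kS passes into the comparison. Within the study, partial against total revision would be unaffected if both types use the same number of inserts.

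4. **Why a per-patient cost matters here.** If a fraction f of patients is converted from total to partial, there are 1/f patients using the sensor for each conversion. For an assumed f of 5%, 10%, 20%, 30% and 50%, this is 20, 10, 5, 3.3 and 2. This shows the asymmetry only and does not fix the sign of any net result.

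5. **Sensor time.** D. Data Collection records OR time for every case, and both sensor sessions take place during the operation. Their minutes are already inside OR time, so the gap concerns the price of the insert.

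**The case against.** The strongest reply is that not named is not the same as not counted. Both lists are worded inclusively, and OR costs are undefined. A device opened and used in theatre belongs there naturally if the hospital buys it. The data sheets that the protocol says are attached are not in the text available, so a sensor cost field may exist. The study is also declared observational, and no net-saving estimate or test is specified. All of this stands, and it makes the understatement conditional. It does not remove the gap: with no payer and no counting rule, sites may treat the insert differently and the reader could not tell.

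Several stronger readings are tempting, and the documents do not support them.

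- **That the protocol itself sets the sensor cost at zero.** The sentence "There are no costs to exceed those associated with the standard of care which currently exists" stands under Risks/Benefits of participation and is most naturally an assurance to participants. It is not a costing rule and does not say who pays.
- **That literature pricing of implants causes the omission.** The sensor is built into a tibial trial and is not an implant. The external source makes the implant part of any saving modelled rather than observed, which is a separate matter.
- **That the time for two sensor sessions is missing.** It lies within OR time, and costing it again would double count against the device.
- **That without the sensor price any conversion at all would show a saving, or that a net loss would be reported as one.** Extra OR time is still counted, a planned partial revision may become total, and the sign also depends on case mix and the external benchmark.

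**Conclusion.** The concern holds in conditional form. The cost lists supporting the economic part of the primary objective do not name a device used in every patient, and no stated cost stream clearly captures it. If the insert is supplied by the sponsor or not billed, sensor-assisted cost is understated by the sensor price per patient, up to 200 times that price at full enrolment. That assumes one insert per patient and none booked to OR costs. Where the hospital books the insert, the understatement is zero.

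No dollar size can be given, and whether the omission would reverse a conclusion cannot be determined from the documents. The point should still be settled before costs are analysed, because the error runs in one direction, favours the device and does not cancel against the external benchmark.

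**What to change.** In D. Data Collection, Cost Data:

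1. Add the VERASENSE insert or inserts used as a separate cost item for every patient, at list or contract price, however they are supplied.
2. Count the item once. Where the hospital has already booked it to OR costs, remove it from there.
3. State the costing perspective and who pays for the sensor in the study.
4. Report cost with and without the sensor, over a range of prices.
5. Do not add sensor-session minutes on top of OR costs.

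The cost is small. The sponsor knows its own price and sites already supply hospital cost data. Each site must also state whether the insert is in its OR costs and how many were opened per case. The downside is that the reported cost becomes slightly less favourable to the device.

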- Patients should present with idiopathic pain and/or instability/stiffness attributed to aseptic loosening, polyethylene wear or malrotation
- Patients able to understand study intent, and agree to study participation
- Patients must be previously implanted with the following cruciate-retaining (CR) or posterior-substituting (PS) total knee systems: Stryker TRIATHLON, Zimmer-Biomet VANGUARD or NEXGEN or Smith and Nephew LEGION or JOURNEY II.

Exclusion criteria:

- No prior revision surgery on operative side
- Ligament insufficiencies, prior surgeries such as PCL reconstructions, posterolateral reconstructions, osteotomies, tibia plateau fractures
- Culture positive aspiration indicating infection of the joint
- ASA class > III
- History of drug or alcohol abuse

Methods/Procedures:

At the time of the revision procedure, the implanted polyethylene will be removed and the corresponding VERASENSE insert type will be placed with the original implanted components still intact. With the patella reduced and the capsule provisionally closed, the knee will be taken through a range of motion to record and observe contact point location and medial and lateral loading at 10, 45, and 90 degrees of flexion as dictated by VERASENSE. Kinematic tracking embedded in the computer software will be engaged to observe femoral rollback patterns in each respective knee. Once the pre-revision “diagnostic” data is recorded, the surgeon will proceed with the standard of care revision procedure. Dependent upon the complexity of the case and output of the VERASENSE data, the surgeon may elect to salvage some or all of the original implanted components or choose to completely revise the knee with the preferred implant system. All revision cases will be cataloged by type (“partial” or “total”). A “partial” revision will be indicated when only the tibial liner is changed or only the tibial liner with the tibial tray or only the tibial liner with the femoral component; A “total” revision will be indicated when all components are completely removed and replaced (tibial tray, femoral component and tibial liner). The VERASENSE sensor will be utilized for final balancing prior to completing the partial or total revision procedures and loading and positional data will be documented once again. All surgical corrections made (i.e.,

bony resections and/or soft tissue releases) during the revision procedure will be documented.

D. Data Collection

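### The primary objective asks why knees fail, but every enrolled knee is already at revision and the sensor is read only then, so the sensor data can describe failed knees and compare failure modes but cannot relate a pattern to failure versus survival

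*Combined protocol and SAP*

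**What the plan says.** Under Purpose of Study, A. Research Objective, the primary aim is to evaluate and "link the possible causes of early TKA revision procedures using intraoperative sensors in effort to understand why knees fail", together with an economic aim that this point does not touch.

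The design, under Research Plan, A. Study Design, is a "Prospective, multicenter, single-cohort evaluation of patients undergoing sensor-assisted revision total knee arthroplasty". The first inclusion criterion, under C. Participants, is "Patients undergoing revision unilateral total knee arthroplasty within the first 5-years of the index procedure". A further criterion reads "Patients should present with idiopathic pain and/or instability/stiffness attributed to aseptic loosening, polyethylene wear or malrotation".

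Methods/Procedures describes two sensor readings, both in the same operation. For the first, the sensor insert is "placed with the original implanted components still intact", and loads and contact points are recorded at three flexion angles. The second comes at the end: "The VERASENSE sensor will be utilized for final balancing prior to completing the partial or total revision procedures". Section D (Data Collection) lists sensor data from before and after the revision and none from the index operation. Its only external benchmark is MEDPAR, for hospital cost, charges and reimbursement.

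Section F compares outcomes data by revision type and applies analysis of variance to groups defined by reason for revision. It does not mention load or contact-point data. Section D describes the dependent variables as the Knee Society Score and the VR-12.

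**The concern.** To learn whether a load pattern contributes to failure, one must know how often that pattern occurs in knees that did not fail. This plan has no such knees, so one side of the comparison is missing.

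Timing is a second gap. The first reading is taken when the knee already has the problem that led to revision. An imbalance seen then could have preceded the loosening, wear or instability, or could have followed it, and nothing recorded earlier would tell the two apart.

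What is at stake is the conclusion the study may draw on the sensor part of its primary objective. The Background already states that proper balance in all knees would improve early failures by 40%. Against that, a result that many early failures were imbalanced could easily be taken as an explanation of failure. The protocol states no limitation about either the missing comparator or the order of events.

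**Working it through.** **The plan's own figure.** There is no calculation to reproduce. The protocol gives up to 200 patients (C. Participants) and alpha 0.05 with a power threshold of 0.7 (Section F), without an effect size, standard deviation or group split. The point is structural and does not depend on the sample size.

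**Step 1. What the data contain.**

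| Needed to relate a pattern to failure | In the plan |
|---|---|
| Failed knees | Yes, all participants |
| Non-failed knees | None |
| Reading before failure | None |
| Reading at revision, original components in place | Yes |
| Reading after correction | Yes, at final balancing |
| External benchmark | MEDPAR, costs only |

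**Step 2. What is estimable.** Let p1 be the prevalence of a pattern in failed knees and p0 its prevalence in non-failed knees. Then

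OR = [p1/(1 − p1)] / [p0/(1 − p0)].

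The study estimates p1 and never observes p0. For illustration take p1 = 0.35. The Background gives 35% as the share of early failures attributed to soft-tissue imbalance; using it as a sensor prevalence is an assumption. The odds in failed knees are 0.35/0.65 = 0.538.

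| Assumed p0 | Odds in non-failed knees | OR for failure |
|---|---|---|
| 10% | 0.111 | 4.85 |
| 20% | 0.250 | 2.15 |
| 35% | 0.538 | 1.00 |
| 50% | 1.000 | 0.54 |
| 70% | 2.333 | 0.23 |

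The choice of p1 does not matter. With an assumed p1 = 0.60 (odds 1.50), values of p0 of 30%, 45%, 60% and 75% give 3.50, 1.83, 1.00 and 0.50. Even the direction is not identified.

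**Step 3. Does enrolling 200 help?** It narrows only p1. The 95% half-width at p1 = 0.35 is 1.96 × √(0.35 × 0.65/200) = 0.066, about ±6.6 percentage points. The uncertainty in p0 is unchanged.

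**Step 4. What the design can support.** Sensor readings can be compared between reasons for revision among failed knees. For two groups of sizes n1 and n2, taking alpha as two-sided (the protocol does not say) and power 0.7, the detectable standardised difference is d = (1.960 + 0.524) × √(1/n1 + 1/n2):

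- 100 v 100: 0.35
- 60 v 140: 0.38
- 40 v 160: 0.44

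The splits are assumed, all 200 are taken to contribute readings, and no allowance is made for multiple comparisons. A contrast of this kind is feasible, but it concerns failure mode, not failure.

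**The case against.** The best reply is that the protocol does not claim what is being denied. The objective speaks of possible causes. The abstract speaks of attempting to relate sensor patterns to the complications that contribute to revision, which is a contrast among revised knees. Section B says the study is observational and not hypothesis driven. No failure risk, odds ratio or causal test is planned, so the odds ratios above measure no error in a planned analysis. A series of failed knees is also a recognised way to study failure mode: the Background cites a review of 781 failed knees.

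Much of this stands. It lowers the severity and limits how far the point may be pressed. Four stronger readings that a reader might infer are not supported:

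- **That the design cannot link sensor patterns to anything about failure.** It can compare them between reasons for revision.
- **That failure processes are shown to have produced the imbalance.** The protocol says nothing to that effect. The Background states the opposite direction, with imbalance showing itself as stiffness, instability or loosening. Malrotation, one of the entry categories, is not said to develop after implantation. The order is unresolved, not reversed.
- **That everything is measured only at revision.** This is true of the sensor data. The Knee Society Score and VR-12 are collected to 12 months, although post-revision scores do not show why the original knee failed.
- **That the sponsor will report causation, or will use the post-revision reading as a normal reference.** The protocol commits to neither.

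What the reply does not do is supply the missing comparator or the time order. Cautious wording leaves the stated aim of learning why knees fail in place as primary. The defence that the study is about failure mode also needs an analysis of sensor data by reason for revision, and Section F names none.

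**Conclusion.** The concern holds in a limited form. All knees enter at revision and all sensor readings come from that operation, so the association between a sensor pattern and failure versus survival cannot be estimated, and the order of imbalance and failure is unresolved. In the illustration, the same 35% is compatible with odds ratios from 4.85 to 0.23. Those figures rest on assumed prevalences; the conclusion rests only on the absence of non-failed knees and of earlier readings.

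The sensor data can support a description of early failed knees and a comparison between failure modes. This should be fixed, because it determines what the study may conclude on its primary objective. It is not a reason to hold the study: the study is declared observational, and no enrolment, procedure or planned test is invalidated.

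**What to change.** 1. Restate the sensor part of the primary objective as describing pre-revision medial and lateral loads and contact-point location at 10, 45 and 90 degrees in early failed knees, and comparing them between reasons for revision. Align the abstract.
2. Add that sensor-by-reason comparison to Section F, naming the sensor variables and the reason groups.
3. State that no causal or failure-risk conclusion will be drawn, because there are no non-failed knees and no reading precedes failure.

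Optionally, if the sponsor already holds sensor readings from surviving primary knees with the same implant systems and the same CR or PS type, these could be shown as a reference. The protocol mentions no such data. The comparison would be descriptive only.

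The cost is a narrower headline claim and a little more analysis work. No new patients or procedures are needed.
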